### [Secondary Outcomes](#)

Secondary outcome measures will be compared between the intervention and control groups and will include the rate of new initiation of antipsychotic medications, patient receipt of the non-pharmacologic IDEA! Strategy handout in post-visit patient instruction, emergency department visits, hospitalizations (including psychiatric hospitalizations), and death within 90 days after the encounter. If patients are seen in the ED or hospitalized for falls within 90 days of being exposed to the intervention, the study team will conduct an implicit medical record review to determine whether these outcomes were unintended consequences of the intervention, considering that patients may have seen other physicians either outside the study or in a different study arm after the initial encounter. The study team will examine whether the intervention led to any unintended consequences such as substitution of other psychotropic medications or reduced time living at home (due to residence in a nursing home or other non-home institution). The study team will also survey clinicians' perceptions of changes in workflow, autonomy, satisfaction, and quality of care.

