### Data Collection Methods

Information sources will include: 1) administrative data found in the UCLA EHR; 2) survey data collected from clinicians in the intervention group; and 3) manual medical record review for patients with ED, falls, or death within 90 days of intervention exposure to assess for potential unintended consequences

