### [Statistical Analyses](#)

The study protocol follows SPIRIT international guidelines and will follow CONSORT guidelines when reporting the trial results. The complete trial protocol can be accessed in the supporting information files. Specifically, the study team will report descriptive statistics to characterize the sample of patients and clinicians included in the study. The study team will review patient charts to display the time series of new antipsychotic prescriptions during the 12 months before intervention rollout, and the 12 months after rollout. Each patient will be monitored for 90 days after their encounter with a physician in either the intervention or control arm, so the follow up period could last up to 90 days after the completion of the trial. The analysis of the primary outcome—total prescription pill-days—will utilize a physician-level linear regression model, with heteroscedasticity-robust standard errors, following prior published approaches. The model will include a fixed effects study arm (intervention vs. control) and baseline number of new prescriptions, adjusting for physician-level characteristics including physician gender and specialty. Analysis of secondary outcomes will proceed similarly, with the sensitivity analyses using different distributions and link functions as appropriate (e.g., a Bernoulli distribution with a logit link for the death outcome). To ensure equal consideration of outcomes among both groups, the study team will include 90-day follow-up for each outcome measure. A p-value of less than 0.05 will be considered

statistically significant. All analyses will follow the intention-to-treat principle and will be performed using SAS v. 9.4 (SAS Institute Inc., Cary, NC).

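### The chart review for unintended consequences covers only patients exposed to the tool, with no control charts or masking stated, so its causal judgments have no comparator; falls are not a separate between-arm outcome, and the two descriptions of the trigger differ.

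*Combined protocol and SAP*

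**What the plan says.** The review is described twice. Data Collection Methods lists as its third information source "manual medical record review for patients with ED, falls, or death within 90 days of intervention exposure to assess for potential unintended consequences". The SAP, under Secondary Outcomes, also counts from exposure: "within 90 days of being exposed to the intervention, the study team will conduct an implicit medical record review". The trigger in full is "If patients are seen in the ED or hospitalized for falls within 90 days of being exposed to the intervention", in which case "the study team will conduct an implicit medical record review to determine whether these outcomes were unintended consequences of the intervention". It adds that reviewers should allow for care the patient may since have had from physicians outside the study or in the other arm.

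Other sections bear on this:

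- **Secondary Outcomes** also plans a randomized comparison: "Secondary outcome measures will be compared between the intervention and control groups". The safety items in it are "emergency department visits, hospitalizations (including psychiatric hospitalizations), and death within 90 days after the encounter". Falls are not named in that list.
- **Statistical Analyses** has patients of physicians in both arms followed for 90 days after the encounter, under intention to treat, with a logit-link sensitivity model for death.
- **Study Design and Setting** defines the two arms by whether the physician is exposed to the tool.
- **Randomization & Blinding** says that clinicians are not blinded. It does not mention chart reviewers.
- **Inclusion Criteria** explains implicit review, in another context, as a matter of expert clinical judgment. No criteria are given for the adverse-event review.

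**The concern.** The reviewers are asked a causal question about single cases: did the tool lead to this event? ED visits, falls and deaths occur in people with ADRD whether or not an alert fires. If only exposed patients' charts are read, nothing shows how often the same reviewers would find a plausible link in patients who never had the alert. If every chart comes from the intervention arm, the arm is also known by construction. Unmasked judgment without criteria can err in either direction: ordinary events can be blamed on the tool, or real harm explained away.

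This matters most for falls, which appear only in the one-arm review. It matters also because Ethical Considerations records a waiver of consent and plans wider adoption of the tool if the trial succeeds. Readers will then look to the safety findings, including the adjudicated ones.

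**Working it through.** **1. Who is reviewed.** Both descriptions start the 90-day window at exposure to the intervention. Could exposure loosely mean the index encounter in either arm? Study Design and Setting uses that word to separate intervention from control, and Statistical Analyses names both arms explicitly when it means both. The natural reading is intervention charts only. No section provides for adverse-event review of control charts.

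**2. What triggers review.**

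| Event | Data Collection Methods | Secondary Outcomes |
|---|---|---|
| ED visit, any cause | Yes | Unclear: the fall qualifier may or may not apply to ED visits |
| Hospitalization for a fall | Yes, as a fall | Yes |
| Fall without ED visit or admission | Yes | No |
| Death | Yes | Not named |

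The mismatch on death is present on either reading. The mismatch on ED visits depends on how the Secondary Outcomes phrase is parsed.

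**3. What has a between-arm comparison.** ED visits, hospitalizations and death do. Falls do not as a separate outcome; those leading to an ED visit or admission are counted within the broader categories. Adjudicated attribution has no comparison at all.

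**4. Number of charts (illustration).** The Sample Size section's analytic sample reproduces: 149 × 0.65 = 96.85, against 96 stated, or 48 physicians per arm. Randomization & Blinding expects 1–2 exposures per physician on average. Assuming one patient per exposure and the same number in the control arm:

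- Patients per arm: 48 × 1 = 48 to 48 × 2 = 96.
- Charts with a trigger event, at an assumed 90-day rate of 10–25%: 48 × 0.10 = 4.8 to 96 × 0.25 = 24, so about 5–24.
- Background events wrongly attributed to the tool, if reviewers did so in an assumed 20%: 4.8 × 0.20 = 0.96 to 24 × 0.20 = 4.8, so about 1–5.

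The documents give no event rate, patient count or attribution rate. The last line shows the mechanism and is not an estimate.

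**5. How informative the randomized comparison may be (illustration).** Two proportions, n per arm, two-sided 0.05, no clustering:

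Power = Φ[(|p₂ − p₁| − 1.96 × SE₀) / SE₁], where SE₀ = √(2p̄(1 − p̄)/n) and SE₁ = √((p₁(1 − p₁) + p₂(1 − p₂))/n).

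For n = 48 and 10% against 20%: SE₀ = 0.0729, SE₁ = 0.0722, so Φ[(0.10 − 0.1429)/0.0722] = Φ(−0.594) = 28%.

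| Assumed baseline risk, doubled | n = 48 | n = 96 |
|---|---|---|
| 5% to 10% | 15% | 26% |
| 10% to 20% | 28% | 49% |
| 20% to 40% | 57% | 86% |

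If baseline risk is low, the valid comparison may well be inconclusive, and the uncontrolled chart judgments would then carry more weight in interpretation.

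**The case against.** The strongest reply is that the randomized comparison is the trial's causal safety assessment and the chart review is a supplementary look at cases. That stands. A reader might infer that the trial has no controlled evidence on ED visits or deaths, or that the review is its only causal safety assessment. The documents do not support this, because both outcomes are compared between arms with the same 90-day follow-up.

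A reader might also see a contradiction with the Statistical Analyses sentence that begins "To ensure equal consideration of outcomes among both groups". That sentence goes on to promise equal follow-up time for outcome measures. It does not promise equal adjudication, so there is no contradiction.

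Nor is it established that deaths would go unreviewed, since Data Collection Methods names them, or that Secondary Outcomes limits ED review to falls, since the wording is ambiguous.

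Three further points have force. The instruction to consider care by other physicians is some guard against over-attribution. No test, stopping rule or adoption decision is tied to the adjudication count. And a masked reviewer cannot say whether an alert caused an event, so extending the present question to control charts would not work. This last point changes the remedy: the question itself must be arm-neutral. None of the three gives the existing judgments a comparator, supplies a between-arm comparison of falls or reconciles the two triggers.

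**Conclusion.** The point holds for the chart review, not for the trial's safety comparison as a whole. As written, only exposed patients receive a causal judgment, no masking or criteria are stated, and background events cannot be told apart from harm in that exercise. Falls lack a separate between-arm comparison, and the two sections disagree on death and are unclear on ED visits.

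The size is modest and cannot be fixed from the documents. The range of about 5–24 reviewed charts rests on assumed patient numbers and event rates, and the 1–5 misattributions on a further assumed rate. The stated sample size, power and significance level are not affected. The change is worth making because it is cheap and removes an avoidable source of attribution bias.

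**What to change.** 1. State one trigger in both Data Collection Methods and Secondary Outcomes, for example any ED visit, fall-related hospitalization or death within 90 days of the index encounter. Define the index encounter identically in both arms.
2. Apply the trigger to index patients in both arms, using the same form and predefined criteria.
3. Ask an arm-neutral question that can be answered with arm and alert details removed where feasible, for example whether the event was related to behavioral symptoms or to psychotropic medication use.
4. Compare the adjudicated proportions between arms, and list fall-related events as a between-arm outcome.
5. Report any unmasked judgment about the alert itself as descriptive only.

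The cost is wording in the protocol and SAP, a short adjudication form, redaction of chart abstracts, and about 5–24 additional control-arm reviews by the same study physicians on the assumptions above. Masking may be incomplete, because order details can sometimes reveal the arm; the report should say how often this happened.

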### [Statistical Analyses](#)

The study protocol follows SPIRIT international guidelines and will follow CONSORT guidelines when reporting the trial results. The complete trial protocol can be accessed in the supporting information files. Specifically, the study team will report descriptive statistics to characterize the sample of patients and clinicians included in the study. The study team will review patient charts to display the time series of new antipsychotic prescriptions during the 12 months before intervention rollout, and the 12 months after rollout. Each patient will be monitored for 90 days after their encounter with a physician in either the intervention or control arm, so the follow up period could last up to 90 days after the completion of the trial. The analysis of the primary outcome—total prescription pill-days—will utilize a physician-level linear regression model, with heteroscedasticity-robust standard errors, following prior published approaches. The model will include a fixed effects study arm (intervention vs. control) and baseline number of new prescriptions, adjusting for physician-level characteristics including physician gender and specialty. Analysis of secondary outcomes will proceed similarly, with the sensitivity analyses using different distributions and link functions as appropriate (e.g., a Bernoulli distribution with a logit link for the death outcome). To ensure equal consideration of outcomes among both groups, the study team will include 90-day follow-up for each outcome measure. A p-value of less than 0.05 will be considered

statistically significant. All analyses will follow the intention-to-treat principle and will be performed using SAS v. 9.4 (SAS Institute Inc., Cary, NC).

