### Sample Size

Power was evaluated using a simulation study. In each simulation, a data set was constructed, combining actual prescribing data from mid-2019 through mid-2020 with simulated data from the subsequent year. The number of total pill days per clinician in the subsequent year was simulated to preserve the mean and standard deviation across clinicians from the prior year, with an assumed year-to-year correlation within clinicians of 0.90. We have previously observed that a small number of providers do a large amount of prescribing, and a large number of prescribers do very little prescribing. The small number of physicians who are likely to continue their high levels of prescribing, leading to high correlation. Clinicians were then randomized into intervention and control arms, with the intervention arm's number of pill days reduced by a constant amount. A linear regression of year 2's number of pill days was fitted with study arm and year 1's number of pill days as predictors. Heteroskedasticity-robust standard errors were used to compute p-values. Significance was defined as a p-value less than 0.05 evaluating the study arm effect in the model, and power was estimated as the percentage of simulations in which a significant difference was obtained. We performed 10,000 simulations to estimate power. Based on historical data, we estimate that about 65% of physicians included in our randomization list will see an eligible patient during the study period. We thus expect our analytic sample to include data from 96 physicians. With 48 physicians randomized to each arm, we will have 80% power to detect a mean reduction of 108 pill days, which is feasible. This simulation power analysis was performed using R v. 3.6.2 (<http://www.r-project.org/>).

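### The 80% power for a 108 pill-day reduction was computed with a model that adjusts for baseline pill-days, but the planned primary model adjusts for baseline prescription count instead

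*Combined protocol and SAP*

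**What the plan says.** **Planned analysis (Statistical Analyses).** The analysed outcome is "total prescription pill-days", in a physician-level linear regression with heteroscedasticity-robust standard errors. On covariates: "The model will include a fixed effects study arm (intervention vs. control) and baseline number of new prescriptions". The model also adjusts for characteristics of the physician, of which gender and specialty are named. Baseline pill-days is not listed.

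**Power (Sample Size).** The simulated data sets were built by "combining actual prescribing data from mid-2019 through mid-2020 with simulated data from the subsequent year". On the outcome: "The number of total pill days per clinician in the subsequent year was simulated", "with an assumed year-to-year correlation within clinicians of 0.90". The regression of year-2 pill-days "was fitted with study arm and year 1's number of pill days as predictors". With 48 physicians per arm the conclusion is that "we will have 80% power to detect a mean reduction of 108 pill days".

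**Outcome definition.** The Primary Outcome section defines days supplied per eligible patient after rollout, set against the preceding 12 months. Study Aims speaks of pill days per patient prescribed. Statistical Analyses and Sample Size both work with totals.

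**Stratification (Randomization & Blinding).** Randomization is stratified by the baseline-year count of new prescriptions (1, 2–3, 4 or more).

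**The concern.** A prescription count and a total of pill-days are different variables, and no section says that one stands in for the other. The difference matters because the stated power depends heavily on the covariate. A correlation of 0.90 means that adjustment removes 0.90² = 81% of the outcome variance and leaves 19%. If the planned covariates together explain less than that, the standard error of the arm effect is larger than the one behind the 80%.

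Bias and type I error are not at stake, and the planned model is a valid one. What is at stake is whether the trial has the power it claims. If it has less, 80% power would apply only to reductions larger than 108 pill-days, and a null result from about 96 physicians would be harder to interpret.

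The unsettled outcome scale adds to this. If the outcome is per patient, the 108 and the 0.90 describe a different quantity from the one to be tested.

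**Working it through.** **Inputs from Sample Size:** significance level 0.05 (two-sided assumed), 80% power, reduction 108, 48 physicians per arm, year-to-year correlation 0.90. The analysed number agrees with the plan's own inputs: 0.65 × 149 = 96.85, stated as 96. The SD of pill-days and the correlation between prescription count and later pill-days are not given.

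**Step 1. The plan's figure.** The 80% cannot be reproduced independently without the SD. One can ask what it implies:
- z = 1.960 + 0.842 = 2.802
- SE of the arm effect = 108 / 2.802 = 38.55
- residual SD = 38.55 / √(2/48) = 188.9
- total SD = 188.9 / √(1 − 0.81) = 433.3

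These values are back-solved, so returning to 80% confirms nothing.

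**Step 2. Other covariate strengths.** Let R be the joint correlation of the planned baseline covariates with follow-up pill-days. Under the normal approximation the SE scales by f = √((1 − R²)/0.19), and the SD cancels.
- Detectable reduction with 80% power = 108 × f
- Power for 108 = Φ(2.802/f − 1.960)

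| R | R² | f | Detectable reduction | Power for 108 |
|---|---|---|---|---|
| 0.90 | 0.81 | 1.000 | 108 | 80% |
| 0.85 | 0.72 | 1.2085 | 131 | 64% |
| 0.80 | 0.64 | 1.3765 | 149 | 53% |

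The 0.85 and 0.80 rows are chosen for illustration. An R above 0.90 would give more than 80%.

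**Step 3. Count as a proxy.** Suppose, as an assumption, that the count predicts year 2 only through year-1 pill-days. Then R = 0.90 × (correlation of count with year-1 pill-days). A correlation of 0.95 gives R = 0.855 and 65% power; 0.90 gives R = 0.81 and 55%. Gender and specialty could recover some precision.

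**Step 4. Change-score reading.** If the outcome were year 2 minus year 1, its variance would be 2(1 − 0.90) = 0.20 of the total variance, against 0.19 with adjustment. Then f = √(0.20/0.19) = 1.026, the detectable reduction is 110.8 and power is 78%. Adjusting for the count as well, under the assumption of Step 3 and a count-to-pill-days correlation of 0.89 to 1.00, gives 79.6% to 80.0%.

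**Step 5. Check by simulation.** Each setting used 10,000 runs, 48 per arm, SD 433.3 and robust (HC1) standard errors.

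| R | Normal data | Lognormal data (assumed) |
|---|---|---|
| 0.90 | 79.2% | 82.1% |
| 0.85 | 63.4% | 70.5% |
| 0.80 | 50.8% | 61.3% |

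The change score at 0.90 with normal data gave 77.0%. Skewness alters the size of the drop but not its direction.

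**The case against.** The mismatch itself is not in dispute. The case against giving it weight runs as follows.

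- **No loss is demonstrated.** Correct. The figures below 80% rest on assumed correlations. Two features of the plan suggest the count may predict well. Sample Size says a few physicians do most of the prescribing. The Intervention section gives the current quetiapine default as 360 pill-days, so count and pill-days would move together if most baseline orders kept such a default. Against this, the same section says physicians may change amounts, and Inclusion Criteria expects more than 75% of physicians to see the tool only 1–2 times a year. Counts would then be small and similar while pill-days could still vary. Neither side fixes the correlation.
- **The power figure does not appear to set the sample size.** The sample is about 65% of the 149 eligible physicians, and 108 is presented as what that sample can detect. This stands: restating power may not change enrolment. It does change what a null result can be taken to mean.
- **The normal approximation may overstate the drop.** Partly so. A lognormal simulation recalibrated to start at the plan's 80% (assumed SD about 450) gave about 80%, 67% and 59% at 0.90, 0.85 and 0.80. The drop is smaller, in the same direction.
- **Adjusting for the count is defensible, since it is the stratification variable.** Agreed, and it should stay. Re-running the simulation with the existing model would cure the inconsistency by itself.
- **The outcome scale is a separate issue.** It is a separate defect, but power cannot be restated until it is settled.

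**Conclusion.** The concern holds. The power statement belongs to a model adjusted for year-1 pill-days and not to the primary model as written; this follows from the text alone. The 80% for 108 pill-days carries over only if the planned covariates together explain about 81% of the variance in follow-up pill-days. It nearly carries over, at about 78%, if the outcome is a change score and the 0.90 is right. However, Statistical Analyses names total pill-days as the outcome, and no section specifies a change score in the regression.

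A loss of power is possible but not shown, and its size cannot be determined from the document. The illustrative fall to 64% or 53% assumes joint correlations of 0.85 or 0.80, a two-sided test at 0.05, the normal approximation and 48 physicians per arm. This should be fixed: the inconsistency is certain, its consequence is confined to precision and interpretation, and the remedy is cheap.

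**What to change.** 1. In Primary Outcome, state whether the outcome is the physician's total pill-days, as Statistical Analyses and Sample Size have it, or pill-days per eligible patient. State also that the follow-up value is analysed with adjustment for baseline. Align Study Aims with this.
2. In Statistical Analyses, add each physician's pill-days in the 12 months before rollout as a covariate, on the same scale as the outcome. Keep the baseline prescription count, on which randomization is stratified.
3. Re-run the simulation with that final model and restate the power or the detectable reduction. Show it over a range of year-to-year correlations, or check the 0.90 against historical data where two full years are available.

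Minimum alternative: keep the model as written and re-run the simulation with it, so that the power statement and the analysis agree.

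Cost: one degree of freedom, a data pull for the 12 months before rollout (a different period from the mid-2019 to mid-2020 data used in the simulation), a simulation re-run, and a restated figure that may be less favourable. The minimum alternative costs only the re-run and the restated figure.
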